#### 25.1.2.3 Recruitment and adherence

Assessed 12 months after recruitment started the following will be reported:

- Number registered
- Number and proportion of those completing their treatment

To meet this criteria at least 12 paticipants should be registered and at least 50% of participants registered completing their active treatment.

#### 25.1.2.4 Futility

The average CRPS pain over the 2 weeks prior to visit 5 (day 120) will be calculated using the Pain diaries days 106 to 119 whereby the average will be:

[the sum of the completed days 106 to 119]/ [number of completed entries].

The baseline pain score, ranging from 0 to 10, is collected on Form 4: Baseline as the average pain from CRPS over the last 24 hours. The average difference will be calculated as the average pain over the 2 weeks prior to visit 5 – baseline measure (day 0). The difference will then be classified for each participant as  $\geq$  2 points of pain reduction on the NRS (rounded to the nearest whole number) or less than 2 points of pain reduction on the NRS, including an increase in score.

After 12 participants have been recruited and completed 4 months treatment period the criteria is met if both of the below are met:

- An average of no pain increase among the completed patients
- At least one participant reporting at least 2 points of pain reduction on the NRS

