10.9 Intervention Discontinuation and Participant Discontinuation/Withdrawal

In consenting to the trial, participants agree to all trial activities including administration of trial intervention and treatment and follow-up assessments/visits and data collection. Every effort should be made to facilitate the completion of these for every recruited participant. If it is not possible to complete these activities (or it is deemed inappropriate) the reasons why should be documented. The following sub-sections describe the different levels of discontinuation/withdrawal.

Premature Discontinuation of Trial Intervention

Participants may discontinue treatment for reasons including, but not limited to:

- Patient-led i.e. request by the patient / legal representative / consultee
- Unacceptable toxicity (see Section 13 for AE reporting)
- Intercurrent illness preventing further treatment.
- CRPS symptom progression which requires discontinuation of therapy or results in inability to continue to comply with study procedures
- Pregnancy
- Death
- Clinician-led:
 - Any change in the participant's condition that justifies the discontinuation of treatment in the clinician's opinion.
 - Reasons of non-adherence or non-compliance with treatment or other trial procedures
 - Participant meets an exclusion criterion (either newly developed or not previously recognised)
 - Participant unable to receive Anakinra for >=7 days consecutively

Discontinuation from Anakinra does not mean discontinuation of the study altogether, and the remaining study procedures, follow up assessment/visits and data collection should be completed as indicated in the protocol unless the patient requests to withdraw from further follow up visits. Data to be collected at the time of discontinuation will include the following:

- 1. Reason for discontinuation (if available)
- 2. Any AEs
- 3. Pain intensity score (NRS)

If a study participant is discontinued from the study early, an End of treatment CRF will be completed describing the reason for discontinuation. In situations where treatment is withdrawn due to an AE, participants will be followed up until resolution of that AE or determination that the participant's condition is stable. All AEs will be followed up until 180 day.

In case of a Participant Withdrawal the participant will be assessed for AEs, if any, and medication use.

Participant Withdrawal from Follow Up

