11 PROGRESSION CRITERIA

Monitoring for clinical trial progress will focus on recruitment and safety. This will be done by the IDSMC.

The following factors will be used to inform the decision to progress into the next stage of the trial:

- 1. **Recruitment**. Assessed 6 months from recruitment start. Initial recruitment rate of 0.5 participants each month per centre for the first 6 months from recruitment start.
- 2. **Safety**. Assessed 12 months from recruitment start (or later if it takes longer for 10 participants to be registered): For the first 10 registered participants, 3 or less reporting persistent pain (greater than 1 week) at injection site of at least moderate intensity (5 or greater on a 0-10 NRS scale) or substantial CRPS pain increase (>=2points NRS), ongoing for >1 month despite and from the time of pain-related treatment stop.
- 3. **Safety**. Assessed 12 months from recruitment start: Consider stopping if 30% or greater of study participants experiencing a serious adverse reaction (SAR).
- 4. **Recruitment and adherence**: At 12 months from recruitment start to have at least 12 participants registered and at least 50% of registered participants completing their active treatment.
- 5. **Futility**. After 12 participants have been recruited and completed 4 months treatment period, an average of no pain increase among completed participants (to visit 5/ 120 day) and at least one participant reporting at least 2 points of pain reduction on the NRS (rounded to the nearest whole number), both these criteria referring to the average pain recordings over the last two weeks before visit 5 / 120 day compared to baseline (0 day).

The IDSMC will use the above progression rules as a guide during regular monitoring with regards to trial progress and will provide a recommendation to the TSC concerning continuing the study. The above are not intended as strict stop/start criteria.

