#### 18.1.2 Assessments of progression criteria

See section "Progression criteria" of the INCA protocol. Assessment of the clinical trial progress will focus on the recruitment and safety of the study, which will be assessed by the IDSMC.

- Recruitment\*. Initial recruitment rate of 0.5 participants each month per centre for the first 6 months from recruitment start.
- Safety\*\*¹. For the first 10 registered participants, ≤3 reporting persistent pain (>1 week) at injection site of at least moderate intensity (≥5 on a 0-10 NRS scale) or substantial CRPS pain increase (≥2points NRS), ongoing for >1 month despite and from the time of pain-related treatment stop.
- Safety\*\*. Consider stopping if ≥30% of study participants experience a serious adverse reaction (SAR).

- 4. Recruitment and adherence\*\*: At least 12 participants registered and ≥50% of registered participants completing their active treatment.
- 5. **Futility**. After 12 participants have been recruited and completed the 4 months treatment period, an average of no pain increase among completed participants (to visit 5 (120 day)) and at least one participant reporting at least 2 points of pain reduction on the NRS (rounded to the nearest whole number), both these criteria referring to the average pain recordings over the last two weeks before visit 5 (120 day) compared to baseline (0 day).

\*Assessed 6 months from recruitment start. \*\* Assessed 12 months from recruitment start.¹or later if it takes longer for 10 participants to be registered).

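### The futility check waits for 12 treatment completers and averages pain over an undefined set of completed patients, so it comes later as more people stop anakinra and leans towards passing if they stop because of pain

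*SAP*

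**What the plan says.** The three places that set out the rule agree on its trigger. SAP 18.1.2 has "After 12 participants have been recruited and completed the 4 months treatment period", and SAP 25.1.2.4 has "After 12 participants have been recruited and completed 4 months treatment period the criteria is met if both of the below are met". The two conditions in SAP 25.1.2.4 are "An average of no pain increase among the completed patients" and "At least one participant reporting at least 2 points of pain reduction on the NRS". Protocol 11 item 5 words the first as "an average of no pain increase among completed participants (to visit 5/ 120 day"). Pain is the mean of the diary entries for days 106 to 119 minus the baseline 24-hour score, and the 2-point reduction is judged after rounding to a whole number.

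Protocol 10.9 lists among the reasons for stopping treatment "CRPS symptom progression which requires discontinuation of therapy or results in inability to continue to comply with study procedures", together with toxicity, patient request and others. It also says "Discontinuation from Anakinra does not mean discontinuation of the study altogether": remaining visits and data collection go on unless the participant withdraws from follow-up, and a pain NRS is taken at discontinuation.

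Neither document defines completed patients for this check. The nearest definition, in SAP 25.2.3.1.1, belongs to the retention outcome and means attending visit 5 (day 120) or the day 180 call.

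**The concern.** The check asks whether pain is, on average, rising in people given anakinra. A rise in pain is itself a listed route out of treatment, so the participants who bear most directly on the question are the ones the rule can lose. There are two consequences.

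- **Timing.** Each person who stops has to be replaced by a later registrant before 12 completers exist. Protocol 14.3 asks the IDSMC whether the data justify further recruitment, and a check that falls after the last registration cannot inform that.
- **Direction.** If completed means treatment completers and people stop because pain worsened, the average is taken over those whose pain did not make them stop. This is the only progression criterion based on average pain change.

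**Working it through.** **Plan's own figure.** Protocol 14.2.1 expects 1 registration per month for 6 months, then 2 per month for 12 months: 6 x 1 + 12 x 2 = 30, which reproduces the planned sample size.

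**Timing.** This needs no assumption about pain. Registrations needed = 12 / completion rate. Month of the n-th registration = 6 + (n - 6)/2 for n above 6. Add 120 days (3.94 months).

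| Completion | Registrations needed | Month of last one needed | Month of check | Registered by then |
|---|---|---|---|---|
| 100% | 12 | 9 | 12.9 | about 20 |
| 75% | 16 | 11 | 14.9 | about 24 |
| 50% | 24 | 15 | 18.9 | 30 (all) |

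The chance that 30 participants ever yield 12 completers (binomial) is 0.90 at 50% stopping and 0.57 at 60%.

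**Direction, by example.** Assume 18 registered: 12 complete with mean change -0.5 and 6 stop with mean change +2. The completer mean is -0.5, which meets the first condition. The mean in all 18 is (12 x -0.5 + 6 x 2)/18 = +0.33, which does not.

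**Direction, by simulation.** The documents give no mean, SD or stopping rate, so these are assumptions: change is normal with mean +0.5 and SD 1.5 or 2.0, and only participants with a rise of 2 or more may stop. The rule is applied to the first 12 completers: mean change at or below 0, and at least one rounded reduction of 2 or more.

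| Of those with a rise of 2 or more | Pass chance, SD 1.5 to 2.0 |
|---|---|
| none stop | 12-19% |
| half stop | 21-38% |
| all stop | 38-73% |

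The all-stop row can be checked by hand. With z = (2 - 0.5)/SD, the completer mean is 0.5 - SD x φ(z)/Φ(z): +0.07 at SD 1.5 and -0.28 at SD 2.0. The share stopping is 1 - Φ(z), or 16% and 23%.

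A different model, in which the chance of stopping rises smoothly with worsening (logistic slope 0.5 per NRS point, mean +0.5, SD 2.0), gives 0.20, 0.39 and 0.62 at 0%, 20% and 40% stopping. With slope 0, so that stopping is unrelated to pain, the pass chance stays at 0.18 to 0.20.

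**Backstops under the same inputs.** Criterion 2 fails if 4 or more of the first 10 registered have persistent injection-site pain or a lasting CRPS pain rise. If each of the 16-23% who stop counted as such a case, the breach chance P(X ≥ 4), X ~ Bin(10, 0.16 to 0.23), is about 6-17%. Criterion 4 needs at least 50% completing, and eventual completion of 77-84% would satisfy it. Read literally at month 12 it is coarse: 18 would be registered and only about 10 could have had 120 days, so 10/18 = 56% is the ceiling even with no stopping.

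**The case against.** The strongest counter-argument has four parts.

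- **Meaning of completed.** A reader might infer that anyone who stops anakinra certainly drops out of the average. The documents do not settle this. Protocol 11 glosses completed with visit 5, and the retention definition in the SAP is visit 5 attendance. On that reading a participant off drug who attends does enter the average. This stands, but the trigger still counts only treatment completers, so the delay remains, and the undefined term itself needs repair.
- **Conditional bias.** A reader might also infer that the check always becomes more favourable as tolerability worsens. It does not: stopping for intercurrent illness, missed doses or other reasons unrelated to pain leaves the pass chance unchanged. The 38-73% row is an extreme case, because every participant with a rise of 2 or more is made to stop. This stands as a limit on the size of the bias.
- **Other safeguards.** Criterion 2 is based on registered participants and is worded with pain-related stopping in mind. In the 18-person example it would be breached with chance about 0.44 if all six rises persisted (hypergeometric). IDSMC reports also cover withdrawals, compliance and safety, and Protocol 11 calls the criteria a guide. This softens the consequences. It does not remove them: criterion 2 requires the CRPS pain rise to last more than a month from the treatment stop, so pain that rose on drug and settled afterwards is not counted there.
- **Filling in values.** Using the single NRS at discontinuation as a day 120 value would carry forward a score taken when pain may have prompted stopping, against the no-imputation stance for outcome analyses in SAP 22.1. This stands, and the fix respects it.

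**Conclusion.** The point holds in two parts. The delay follows from the trigger alone: about 2 months at 75% completion and 6 months at 50%, by which time recruitment is over on the planned schedule. The bias towards passing is conditional on completed meaning treatment completers and on stopping being related to worsening pain, which Protocol 10.9 foresees. Under the assumed mean of +0.5 and SD 1.5 to 2.0, the pass chance goes from 12-19% to 21-38% if half of those with a rise of 2 or more stop, with 38-73% as the upper case. The documents supply none of those inputs, so the figures show direction and scale and are not predictions. Because the rules are guides and other criteria catch part of the problem, this is a change that should be made rather than a flaw that invalidates the monitoring. A guide still ought to show the committee a figure that is not selected on treatment completion.

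**What to change.** Amend Protocol 11 item 5 and SAP 18.1.2 and 25.1.2.4 as follows.

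1. Trigger the check when the first 12 registered and treated participants have reached day 120, whether or not they are still on anakinra. On planned accrual this is about month 12.9 at any stopping rate.
2. Report the average change and the number with a 2-point reduction over all of those with day 106-119 diary data, on or off drug.
3. Show the completer-only figures beside them, with completed defined, the number excluded and their reasons for stopping.
4. For those without day 106-119 diaries, list the discontinuation NRS separately or use it only in a labelled sensitivity figure. It should not replace the 14-day mean.

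The cost is wording in one protocol item and two SAP sections, and a short addition to the IDSMC report. No new data are needed, because diaries and follow-up already continue after stopping. The downside is that the all-treated figure mixes on-drug and off-drug pain, may understate a rise that settled after stopping, depends on diaries being returned, and may look less favourable than the completer-only figure. That is why both should be shown.

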#### 25.1.3 Formal Interim Analysis

Not applicable.

#### 25.2 Final Analysis

#### 25.2.1 Levels of significance and multiplicity

As INCA is a feasibility phase II study, study outcomes are focused on safety/tolerability, recruitment and protocol/ treatment adherence, therefore, all outcomes will be summarised using appropriate summary measures.

CLINICAL TRIALS CENTRE LCTC

#### 25.2.2 Primary Outcome(s)

To determine the safety and tolerability of Anakinra in patients with refractory moderate to severe CRPS.

#### 25.2.2.1 Derivation

This is defined as the proportion of patients with no serious or condition-specific AEs. Pre-determined potential condition-specific AEs are:

- Persistent pain at injection site (greater than 1 week) of at least moderate intensity (≥5 on a 0-10 NRS scale)
- Increase in CRPS associated pain (≥ 2points NRS), ongoing for >1 month.

Serious or condition-specific AEs are indicated on the following case report forms (CRFs) INCA Premature discontuation form, INCA Withdrawal form, Form 6: Follow up, Form 5: Telephone follow up and Form 7: Final telephone follow up. Further details of the events are collected on INCA Adverse Events form and INCA Serious safety event report form.

Patients will be classified as either having experienced at least one serious or condition-specific AE or experienced no serious or condition-specific AEs. The proportion of patients with no serious or condition-specific AEs will be defined as:

[total number of patients to have experienced no serious or condition-specific AEs]/[total number of registered patients].

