13.7 Notes on Safety Event Recording

The following events must be recorded for the purposes of the trial:

- An exacerbation of a pre-existing illness
- An increase in frequency or intensity of a pre-existing episodic event/condition

- A condition (even though it may have been present prior to the start of the trial) detected after trial drug administration
- Continuous persistent disease or symptoms present at baseline (0 day) that worsens following the administration of the study/trial treatment
- Laboratory abnormalities that require clinical intervention or further investigation (unless they are associated with an already reported clinical event).
- Abnormalities in physiological testing or physical examination that require further investigation or clinical intervention
- Injury or accidents
- Pregnancy (See section 13.8 for more details)
- Weight loss of ≥4% within 4 months

Do not record:

- Medical or surgical procedures the condition which leads to the procedure is the AE
- Pre-existing disease or conditions present before treatment that do not worsen
- Situations where an untoward medical occurrence has occurred e.g. cosmetic elective surgery¹
- Overdose of medication without signs or symptoms*2
- The disease being treated or associated symptoms/signs unless more severe than expected for the participant's condition

*N.B. If overdose occurred **with** resulting signs and symptoms that meet the protocol criteria for AE/AR/SAE/SAR/SUSAR then they should be reported accordingly (see section 13.12 for more information) and the overdose highlighted to the LCTC team.

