25.1.2.2 Safety

The frequency and proportion of participants, denominator used as the number registered, who have experienced the below will be summarised:

persistent pain (greater than one week) at the injection site of at least moderate intensity (≥

5 on a 0-10 NRS scale)

• a substantial CRPS pain increase of  $\geq$  2 points NRS, ongoing for more than 1 month despite

and from the time of pain related treatment stop.

SARs

The substantial pain increase will be calculated as: CRPS pain at day X – CRPS pain at day (X-30), where X is >30. Persistent pain will be derived from the pain dairies and adverse events. Both substantial pain increase and persistent pain are collected throughout the trial as Adverse events and are particularily asked about at each visit (see forms 5 – Telephone Follow up, 6 Follow up and 7 Final Telephone follow up). The yes/no response at each visit and the derived substantial pain increase/persistent pain will

both be used to ensure all events are captured.

If 3 or less patients report persistent pain or substantial pain increase across the first 10 participants

registered this criteria will have been met.

However, stopping will be considered if 30% or more of study participants experience an SAR in the first 12 months of recruitment.

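### The primary outcome's CRPS-pain component is derived from forms with no stated score check, although the related interim criterion combines form answers with recorded scores

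*SAP*

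**What the plan says.** **Final primary outcome (SAP 25.2.2.1).** The CRPS-pain component is numeric: "Increase in CRPS associated pain (≥ 2points NRS), ongoing for >1 month". On where events come from, the SAP says "Serious or condition-specific AEs are indicated on the following case report forms (CRFs") and names the premature discontinuation form, the withdrawal form, and "Form 6: Follow up, Form 5: Telephone follow up and Form 7: Final telephone follow up". Further detail comes from the adverse event and serious safety event forms. The result is "total number of patients to have experienced no serious or condition-specific AEs]/[total number of registered patients". The section uses no diary or score calculation and does not refer back to 25.1.2.2. SAP 25.2.2.2 adds only a sensitivity analysis that removes participants with protocol deviations of concern.

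**Interim safety criterion (SAP 25.1.2.2).** Here a score derivation is given: "The substantial pain increase will be calculated as: CRPS pain at day X" minus CRPS pain 30 days earlier, for X above 30. In addition, "Persistent pain will be derived from the pain dairies and adverse events". The two sources are then joined: "The yes/no response at each visit and the derived substantial pain increase/persistent pain will" both be used, with the stated aim of catching every event.

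**Scores available (Protocol 10.7).** The diary is weekly from day 0 to 90, daily from day 90 to 120 and weekly from day 120 to 180. Table 4 also schedules a CRPS-pain NRS at every post-baseline visit and call.

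**The concern.** The component is defined by a size (2 points) and a duration (more than 1 month), and the trial records the scores needed to check both. For the interim criterion the SAP does not rely on the form answer alone, even though the question is put directly at each visit. For the headline result it gives no such check. A programmer working from 25.2.2.1 would use the forms, while one who carried 25.1.2.2 forward would use forms and scores, and the two could report different primary results. SAP section 5 says the plan should explain data handling well enough for the analysis to be replicated.

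Protocol 14.2 says the safety outcome will help judge whether a larger randomised trial is feasible. An event that the forms miss can only raise the event-free proportion.

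**Working it through.** The plan states no figure on this point, so there is none to reproduce. The check compares the two derivations and works out the effect of one reclassified participant.

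**Step 1. Apply both rules to example score paths.** The paths are illustrative. Assume that visit scores are used, that diary entries between visits agree with them, and that every form answer is no. The interim rule flags a participant if score(X) − score(X − 30) is 2 or more, for X = 60, 90 or 120.

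| Scores at days 0, 30, 60, 90, 120 | 30-day differences at X = 60, 90, 120 | Interim formula | Rise over day 0 at days 60, 90, 120 | Final result from forms |
|---|---|---|---|---|
| 6, 6, 8, 8, 8 | 2, 0, 0 | flagged | 2, 2, 2 | event-free |
| 6, 6, 8, 6, 6 | 2, −2, 0 | flagged | 2, 0, 0 | event-free |
| 6, 7, 8, 9, 9 | 1, 1, 0 | not flagged | 2, 3, 3 | event-free |
| 6, 8, 8, 8, 8 | 0, 0, 0 | not flagged | 2, 2, 2 | event-free |

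- Row 1 is the core case. Scores are 2 points up from day 60 to day 120, which meets the numeric definition. The interim formula flags the participant, but the final derivation as written does not.
- Row 2 shows the interim formula firing on a rise that need not have lasted more than 1 month. Event-free in the final result may then be correct.
- Rows 3 and 4 meet the numeric definition and are missed by both rules. The interim formula misses gradual rises and, on visit scores, rises before day 30, because its first difference is day 60 minus day 30.

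**Step 2. Size per participant.** With N = 30 (Protocol 14.2), one participant moved from event-free to event changes the proportion by 1/30 = 3.3 points, provided that participant has no other qualifying event.

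**Step 3. Illustration.** Assume 27 of 30 are event-free by the forms. Intervals are exact (Clopper-Pearson) 95%.

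| Participants found by scores alone | Event-free | Proportion | 95% interval |
|---|---|---|---|
| 0 | 27/30 | 90.0% | 73.5 to 97.9% |
| 1 | 26/30 | 86.7% | 69.3 to 96.2% |
| 2 | 25/30 | 83.3% | 65.3 to 94.4% |
| 3 | 24/30 | 80.0% | 61.4 to 92.3% |

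**Step 4. Range under assumed capture rates.** Inflation is at most true event rate × (1 − share captured by the forms). At a 20% true rate with 90%, 70% or 50% captured, it is 0.20 × 0.10 = 2 points, 0.20 × 0.30 = 6 points, or 0.20 × 0.50 = 10 points. At a 10% true rate the range is 1 to 5 points, and at 30% it is 3 to 15. Neither the event rates nor the capture rates come from the documents. The figures are upper bounds because someone with a serious or injection-site event is already counted as an event.

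**The case against.** Several points on the other side are fair.

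- **The SAP does not exclude scores.** A reader might infer that the final outcome is by rule taken from forms alone. Section 25.2.2.1 says where events are indicated and is silent on scores. The defect is that silence.
- **The answers are not unaided recall.** A reader might infer that participants must judge a 2-point rise from memory. SAP 25.1.2.2 says both events are specifically asked about at each visit, Protocol 10.7 has clinic pain assessed from the diaries, and Table 4 puts an NRS at all nine post-baseline contacts (four visits and five calls). A sustained rise with every answer no would require staff to overlook scores they are collecting. This stands and limits the risk.
- **The interim event is not the same event.** SAP 25.1.2.2 and Protocol section 11 require the CRPS-pain increase to persist despite, and be timed from, a pain-related treatment stop. The primary outcome has no such condition. A reader might infer that the final definition is simply a less sensitive version of the interim one. On this condition the interim definition is the narrower, so the two can differ in either direction.
- **The interim formula is a poor benchmark,** as rows 2 to 4 above show.
- **Protocol 13.7 is weak evidence of under-recording.** It tells sites not to record "The disease being treated or associated symptoms/signs unless more severe than expected" for the participant's condition. That line carries its own exception, and the same section asks for worsening baseline symptoms to be recorded.
- **The analysis is descriptive.** Protocol 14.1 states no formal hypotheses, and the final proportion has no success threshold.

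What survives is the gap itself: a numerically defined component of the primary outcome has no stated numeric check, while the SAP uses one for the related interim criterion.

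**Conclusion.** The concern holds in limited form. As written, SAP 25.2.2.1 lets a participant whose scores meet the CRPS-pain definition count as event-free if the forms say no. The cost is 3.3 points of the headline proportion for each such participant with no other qualifying event. This assumes N = 30 and an analyst who takes 25.2.2.1 as the complete derivation. The documents give no basis for estimating how many participants would be affected, so the wider ranges in the working are illustrations.

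A reader might infer an established upward bias in the reported safe proportion. The documents do not support that: they show a route by which events could be missed, alongside prompted questions and repeated scoring that make it less likely. The change is still worth making before the final analysis, because it uses data already collected and makes the headline figure reproducible.

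**What to change.** 1. In SAP 25.2.2.1, count the CRPS-pain component as met if it is recorded on a CRF **or** if diary/NRS scores stay 2 or more points above a named pre-treatment reference for more than 1 month.
2. Pre-specify that reference. The candidates are the Form 4 24-hour score, which SAP 25.1.2.4 and 25.2.3.2.1.1 already use as baseline, and the mean of the 7-day pre-baseline diary. State how missed entries within the month are handled; the no-imputation rule in SAP 22.1 does not settle this.
3. Report counts by source (form only, scores only, both), so that the form-only result stays visible.
4. Do not carry the 30-day difference into the final analysis. Correct it in SAP 25.1.2.2, or justify it there and name the scores it uses. Protocol section 11 does not contain the formula, so this is a SAP change.
5. Reconcile the pain-related treatment-stop condition in Protocol section 11 and SAP 18.1.2 and 25.1.2.2 with its absence from Protocol section 9 and SAP 15.1 and 25.2.2.1, or explain the difference. Changing the progression criterion itself would need a protocol amendment.
6. Reconcile the source for injection-site pain: diaries and adverse events in SAP 25.1.2.2, forms in 25.2.2.1. Protocol 10.3 and 10.7 describe the diary only as recording pain intensity.
7. As a minor clarification, say in Protocol 13.7 that its exclusion of disease symptoms does not apply to the condition-specific events.

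The main cost is SAP wording and a short derivation on existing data; item 7 needs a line in the protocol. The event-free proportion may fall slightly.
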